5.2.3. Safety Population

For Phase 1b part, safety population includes all subjects who were enrolled and received at least one dose of study treatment. Subjects will be classified according to the treatment received, where treatment received is defined as the assigned dose level/schedule if it was received at least once, or the first dose level/schedule received if assigned treatment was never received. The safety population will be used for all safety analyses and drug exposure.

For Phase 2, the safety population includes all randomized subjects who received at least 1 dose of study treatment. Subjects will be analyzed according to the initial treatment actually received.

5.2.4. Pharmacokinetics Population

The PK population includes all subjects who enroll and receive at least one dose of study drug (AG-221/AG-120) and have at least 1 measurable concentration datum of study drug.

5.2.5. Full Analysis Population

Full analysis population (FAP) includes all subjects who were enrolled and received at least 1 dose of study treatment. Subjects will be classified according to the assigned dose level and schedule. FAP is the primary analysis population and will be the default analysis set for all analyses except the safety analyses, unless otherwise specified. This population is defined for the Phase 1b part only.

5.2.6. DLT-Evaluable Population

Subjects who take at least one dose of study drug in phase 1b dose-finding stage and either have a DLT during Cycle 1 regardless of amount of study drug exposure, or have no DLT and complete at least 75% of AG-120 or AG-221 doses (21 out of 28 days) and a minimum of 5 doses of azacitidine, and at least 50% of the planned combination doses for AG-120 or AG-221 and azacitidine administered together (in the same day for 4 out of 7 days) in the first 28 days from Cycle 1 Day 1 and are also considered by the Clinical Study Team to have sufficient safety data available to conclude that a DLT does not occur during Cycle 1. A subject diary will be used during outpatient treatment to record details around AG-120 and AG-221 dosing. Subjects in this population set will be denoted as evaluable for DLT assessment and RCD estimation. This population is defined for the Phase 1b Dose-finding stage only.

5.2.7. Evaluable Analysis Population

For Phase 1b, Evaluable Analysis Population (EAP) includes all subjects in the FAP for whom the baseline response assessment and at least one post baseline response assessment at Day 28 or later are available and evaluable. The clinical activity of AG-221/AG-120 combined with azacitidine will be primarily assessed in the FAP. Additional efficacy analyses may be conducted for the EAP.

For Phase 2, EAP is defined as all subjects in the ITT for whom the baseline response assessment and at least one post baseline response assessment at Day 28 or later are available and evaluable. The clinical activity of AG-221 combined with azacitidine will be primarily assessed in the ITT. Additional efficacy analyses may be conducted for the EAP.

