- p Whenever response/diagnosis is assessed in the Follow-up Period (ie, every 8 weeks [ $\pm$  28 days]). See Section 6.3 for details.
- q Day 1 ( $\pm$  14 days) of every 3rd cycle (eg, Cycles 3, 6, 9, etc) or more frequently per standard institutional practice. Not necessary for the EOT Visit if last performed within 14 days.
- r Day 1 ( $\pm$  28 days) of every 6th cycle (eg, Cycles 6, 12, 18, etc) or more frequently per standard institutional practice. Not necessary for the EOT Visit if last performed within 28 days.
- s Continuous starting after signing ICF through 28 days after the last study treatment. See Section 6.4.1 for details.
- t Including type, number of units, reasons, and date of transfusions taken  $\leq$  8 weeks prior to the start of study treatment through 28 days after the last study treatment. Thereafter, transfusions will continue to be collected until the next AML therapy after discontinuation from study treatment, death, lost to follow-up, withdrawal of consent for further data collection, or the End of Trial, whichever occurs first.
- v In addition to the frequency specified in the table, samples will also be collected if clinically indicated (eg, confirmation of CR/CRi/CRp, morphologic relapse after CR/CRi/CRp, or progression by a repeated bone marrow assessment at least 1 month later) or required for toxicity assessment. A sample of bone marrow and peripheral blood must also be sent at these time points for central pathology review.
- w Within 7 days prior to Day 1 of Cycle 2. The assessment is not required at Day 1 of Cycle 1.
- x Within 7 days prior to Day 1 of Cycle 3. The assessment is not required at Day 1 of Cycle 4.
- y Within 7 days prior to Day 1 of Cycle 5 and Day 1 of every 2nd cycle thereafter (eg, Cycles 7, 9, etc).
- z Not necessary for the EOT Visit if last performed within 28 days.
- bb A bone marrow biopsy can be collected in conjunction with an aspirate if it is standard institutional practice. A bone marrow biopsy must be collected if adequate aspirate is not attainable.
- cc A standard cytogenetic metaPhase preparation will be prepared if the bone marrow aspirate is obtained for assessing CR, morphologic relapse, or progressive disease and will be sent to the local laboratory for cytogenetic analysis.
- dd Including diary cards. See Section 7.6 for details.

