## 6.5. Efficacy

### 6.5.1. Response

Bone marrow aspirate (or biopsy if adequate aspirate is not attainable) samples will be collected for assessing response. The site must ensure peripheral blood for central hematology is collected and sent at the time of every bone marrow collection. As specified in the Table of Events, [Table 4](#), the frequency is within 7 days prior to study treatment administration on Cycles 2, 3 and every 2nd cycle thereafter (eg, Cycles 5, 7, 9, etc), and if clinically indicated (eg, confirmation of CR/CRi/CRp, morphologic relapse after CR/CRi/CRp or progression as defined in modified IWG AML response criteria ([Cheson, 2003](#)) ([Appendix F](#)) and International Working Group response criteria in myelodysplasia ([Cheson, 2006](#)) by a repeated bone marrow assessment at least 1 month later) or required for toxicity assessment. A bone marrow biopsy can be collected in conjunction with an aspirate if it is standard institutional practice or if clinical indicated (eg, evaluation of bone marrow cellularity). Whenever a bone marrow sample is collected, a peripheral blood smear is to be prepared. In addition, whenever a bone marrow aspirate is obtained for confirming CR/CRi/CRp, morphologic relapse after CR/CRi/CRp or progression, a

standard cytogenetic metaPhase preparation will be prepared and sent to the local laboratory for cytogenetic analysis. A bone marrow biopsy can be used for cytogenetics testing if adequate aspirate is not attainable.

Bone marrow aspirate and/or biopsy and peripheral blood smear collected after the start of study treatment must be available for both local and central pathology review. The retrospective central pathology review will require a set of duplicate slides for each bone marrow collection time point including BMA, peripheral blood smear, and BMB if performed. The central pathology review will be conducted by personnel blinded to study treatment.

Response to treatment and HI will be assessed by the investigators according to modified IWG AML Response Criteria (Cheson, 2003) (Appendix F) and IWG myelodysplastic syndromes HI criteria (Cheson, 2006) (Appendix G), respectively.

Instructions for submission slides of bone marrow aspirate (and/or biopsy) and peripheral blood smear for central pathology review are provided in the Study Reference and Study Central Laboratory Manuals.

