#### **Evaluable Analysis Population**

Evaluable Analysis Population (EAP) includes all subjects in the ITT for whom the baseline response assessment and at least one post baseline response assessment at Day 28 or later are available and evaluable. The clinical activity of AG-221 combined with azacitidine will be primarily assessed in the ITT. Additional efficacy analyses may be conducted for the EAP.

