5. GENERAL STATISTICAL CONSIDERATIONS

5.1. Reporting Conventions

The following reporting conventions apply generally to tables, listings, and figures:

- Data from all study centers will be combined for analysis;
- In general, analyses for Phase 1b subjects will be done by AG-120 + AZA and AG-221 + AZA and by dose cohort in dose-finding, total in dose-finding, dose cohort in expansion (only for AG-120 + AZA), and total for AG-120 + AZA. For Phase 2, AG-221+AZA versus pooled AZA alone will be compared.
- P-values will be rounded to 4 decimal places; P-values that round to 0.0000 will be presented as '<0.0001' and p-values that round to 1.000 will be presented as '>0.9999
- Confidence intervals (CIs) will be presented as two-sided 95% CIs unless specified differently in specific analysis;
- Summary statistics will consist of the number and percentage of subjects (or cycles, if appropriate) in each category for discrete variables, and the sample size, mean, median, standard deviation, first quartile (Q1), third quartile (Q3), minimum, and maximum for continuous variables;
- All mean and median values will be formatted to one more decimal place than the measured value. Standard deviation values will be formatted to two more decimal places than the measured value;
- All percentages will be rounded to one decimal place. The number and percentage of responses will be presented in the form XX (XX.X%), where the percentage is in the parentheses. In case of zero frequency, the percentage will not be displayed;
- All listings will be sorted for presentation in order of treatment arm, study center, subject, and date/time of procedure or event and will be presented separately for each phase. Subjects who are screened but not randomized will be listed separately as a non-randomized group;
- All analysis and summary tables will have the analysis population sample size (i.e., number of subjects);
- The day of the first dose of any study drug will be defined as Day 1.
- Unless noted otherwise, baseline value will be defined as the last non-missing value prior to the start of study treatment on Day 1 of Cycle 1. For subjects who are randomized but not treated, the baseline will be the assessment value on or prior to randomization date.
- To summarize efficacy/safety data by visit, the post-baseline results will be summarized by the scheduled visit or the derived visit as appropriate.
- Calculation of Cycles:

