Abbreviations: AML = acute myeloid leukemia; β-hCG = β-subunit of human chorionic gonadotropin; BMA = bone marrow aspirate; BMB = bone marrow biopsy; BSA = body surface area; CR = morphologic complete remission; ██████████ ECHO = echocardiogram; eCRF = electronic case report form; ECG = electrocardiogram; ECOG = Eastern Cooperative Oncology Group; EORTC= European Organization for Research and Treatment of Cancer; FCBP = female of childbearing potential; EOT = End of Treatment; HI = hematologic improvement; HSCT = hematopoietic stem cell transplantation; ICF = informed consent form; IDH2 = isocitrate dehydrogenase isoform 2; IP = investigational product; IWG = International Working Group; IWRS = interactive web response system; MRD = minimal residual disease; MUGA = multi-gated acquisition; PK = pharmacokinetics; PB = peripheral blood; RNA= Ribonucleic acid; SOC = standard of care; UGT1A1 = uridine diphosphate-glucuronosyltransferase 1 family, polypeptide A1

^a One cycle (one month) is considered as 28 days (ie, 4 weeks). Unless noted otherwise, an administrative window of ± 3 days is permitted for all subsequent visits after the start of study treatment in each treatment cycle in the Treatment Phase. Day 1 of Cycles 2 and beyond may be delayed from Day 28 of the prior cycle in order for subjects to recover from toxicity and meet criteria for initiating each treatment cycle (Section 7.2 in Protocol). The study visit window for EOT or monthly-scheduled survival follow-up is ± 7 days.

^b See Section 6.2.3 in Protocol for details.

^c Including informed consent for mandatory genetic testing ██████████.

^d The subject should start study treatment (ie, Day 1 of Cycle 1) within 3 days after enrollment or randomization.

^e Subject should continue to be eligible for study entry prior to the start of study treatment on Day 1 of Cycle 1.

^f Cycle 1 only.

^g See Section 6.1 in Protocol for details regarding collecting BMA, BMB, PBS, and cytogenetics at screening for assessing AML diagnosis, collecting BMA and PB at screening for potential retrospective confirmation of mutational status, and collecting BMA and PB at screening for pharmacodynamics ██████████.

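### The evaluable population's Day 28 cut-off rejects most of the nominal window for the first scheduled response marrow, so some on-schedule assessments do not count

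*SAP*

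**What the plan says.** SAP 5.2.7 admits a patient to the EAP, in either phase, only with an evaluable baseline assessment and "at least one post baseline response assessment at Day 28 or later are available and evaluable". Protocol 9.2.1 and 9.2.2 (Phase 1b) and 9.2.3 (Phase 2) carry the same rule. No tolerance is given.

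The first on-treatment marrow and the first IWG response assessment are scheduled by footnote w of the table of events (Protocol Table 4, repeated in SAP 17.3): "Within 7 days prior to Day 1 of Cycle 2. The assessment is not required at Day 1 of Cycle 1". Protocol 6.5.1 agrees: "the frequency is within 7 days prior to study treatment administration on Cycles 2, 3 and every 2nd cycle thereafter".

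SAP 5.1 fixes the day count: "The day of the first dose of any study drug will be defined as Day 1". Both tables of events set a 28-day cycle, with a general visit window of 3 days either way. They allow the start of Cycle 2 to slip: Cycles 2 and "beyond may be delayed from Day 28 of the prior cycle in order for subjects to recover from toxicity".

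SAP 10.1 places the primary ORR test on the ITT population and runs sensitivity analyses on both the mITT and the EAP. SAP 10.2 also uses the EAP as a sensitivity set for the Phase 1b response endpoints.

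**The concern.** A site that follows the schedule will usually take the first response marrow on a day that the EAP rule does not recognise. That does no harm to a patient who is assessed again. A patient with an evaluable Day 24 marrow who dies, withdraws or changes therapy before another assessment is treated as not evaluable, although the protocol was followed.

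The rule also sits badly with the rest of the plan. The response criteria (Protocol Appendix F, SAP 17.4) reserve the not-evaluable category for patients with no assessment after treatment. The SAP's mITT definition (5.2.2) asks for one response assessment after randomisation and sets no day. The same Day 24 marrow therefore counts in one supportive set and not in the other.

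Patients who leave this early are likely to be mostly non-responders. The amendment rationale for Protocol 7.2.1.1 and 7.2.1.2 says a first response may take 4 to 6 cycles. Removing them raises the EAP response rate. The selection happens after randomisation in an open-label trial, so the arms may lose different numbers. The loss would also be hard to see, because SAP Section 6 plans a listing of reasons for exclusion from the mITT but none for the EAP.

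**Working it through.** **1. The plan's own figure.** The documents give no figure for the EAP. The only design figure behind ORR is 75% power (SAP 4.4) for 50% versus 30%, with 66 and 33 patients and two-sided alpha 0.2.

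- Pooled rate = (9.9 + 33)/99 = 0.433.
- Null SE = √(0.433 × 0.567 × (1/33 + 1/66)) = 0.1057.
- Alternative SE = √(0.21/33 + 0.25/66) = 0.1008.
- Power = Φ((0.20 − 1.282 × 0.1057)/0.1008) = 73.9%.

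The unpooled form gives 75.9%, and exact enumeration of the chi-square test gives 75.3%. The stated 75% is reproduced. It rests on ITT and is unaffected by the EAP rule.

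**2. The assessment window in study days.** First dose is Day 1, so nominal Cycle 2 Day 1 = 1 + 28 = Day 29. The seven days before it are Days 22 to 28. Only Day 28 meets the cut-off; Days 22 to 27, six of the seven, do not. If Cycle 2 starts s days late, the window is Days 22 + s to 28 + s, and the failing days number 6 − s, with a minimum of 0.

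| Cycle 2 start relative to Day 29 | Window | Days failing the cut-off |
|---|---|---|
| 3 days early (Day 26) | 19–25 | 7 of 7 |
| On time | 22–28 | 6 of 7 |
| 1 day late | 23–29 | 5 of 7 |
| 3 days late | 25–31 | 3 of 7 |
| 5 days late | 27–33 | 1 of 7 |
| 6 or more days late | 28–34 or later | 0 of 7 |

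The early row applies only if the 3-day visit window is read as permitting an early cycle start.

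**3. The next chance to qualify.** Nominal Cycle 3 Day 1 is Day 57, so the next scheduled marrow falls on Days 50 to 56. The end-of-treatment marrow is waived if one was done in the previous 28 days. A Day 22 marrow covers that visit to Day 50, and a Day 27 marrow to Day 55. After treatment stops, response follow-up ends at progression, relapse or second-line therapy (Protocol 3.1.2.4).

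**4. Effect on ORR (illustration only).** The documents give no rate of early loss, so the number lost, k, is an assumption, and every lost patient is taken to be a non-responder. ORR in the EAP = responders/(n − k), starting from 10/33 and 33/66, the whole-patient counts nearest the planning rates.

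| k lost | Azacitidine alone | AG-221 + azacitidine |
|---|---|---|
| 0 | 10/33 = 30.3% | 33/66 = 50.0% |
| 2 | 10/31 = 32.3% | 33/64 = 51.6% |
| 4 | 10/29 = 34.5% | 33/62 = 53.2% |
| 6 | 10/27 = 37.0% | 33/60 = 55.0% |

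The difference starts at 19.7 points. Six lost from control alone gives 50.0 − 37.0 = 13.0 points. Six lost from the combination arm alone gives 55.0 − 30.3 = 24.7 points.

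In proportional terms, from 30% and 50%, a 10% loss in both arms gives 0.30/0.90 = 33.3% and 0.50/0.90 = 55.6%, a difference of 22.2 points. Losing 15% of control and 5% of combination gives 17.3 points; the reverse gives 27.2.

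**The case against.** A reader might infer that on-schedule early failures as a class are dropped. The documents do not support that. Progressive disease has to be confirmed by a further assessment a month or more later (Protocol Appendix F), so a patient with confirmed progression has an assessment after Day 28 and stays in if it is evaluable. A patient who stops treatment before progression, relapse or second-line therapy continues to have marrow assessments every 8 weeks (Protocol 6.3) and will usually qualify. What remains is a narrower group: early deaths, unconfirmed progressions, withdrawals and early switches, each with a Day 22 to 27 marrow and nothing after it.

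Nor is six days in seven a fixed fraction. It is the nominal case and shrinks with each day Cycle 2 is delayed. A pre-dose marrow on Day 29 itself, if a site takes one then, would also pass.

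The EAP is a supportive set, one of two, and SAP 5.2.7 says analyses on it may be done. Any response-evaluable set leaves out patients who die before the first marrow; only the Day 22 to 27 increment is due to this cut-off. The loss counts above are assumptions, and six controls would be 18% of that arm.

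All of this stands and limits the size of the problem. It does not remove the mismatch. SAP 5.1 lets by-visit summaries use the scheduled visit, but nothing extends that to EAP membership. SAP 10 and 10.1 commit to running the EAP analyses.

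**Conclusion.** The Day 28 cut-off and the assessment schedule conflict on the documents' own day numbering. Followed literally, the rule removes protocol-compliant patients from a planned sensitivity analysis. If those patients respond less often than the rest of their arm, as is likely, EAP response rates are pushed up. By how much cannot be estimated from the documents.

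Two stronger conclusions should be resisted. One is that the rule flatters AG-221: the treatment difference can move either way, and loss confined to control would shrink it. The other is that the trial's main result is at risk: affected patients remain in the ITT denominator, the 75% power is unchanged, and the mITT has no such cut-off, although its other criteria still apply.

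This is a wording defect in a supportive population, and worth correcting because correction is cheap. Confidence is high in the day arithmetic and low in any particular size of effect.

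**What to change.** In SAP 5.2.7 and Protocol 9.2.1 to 9.2.3, replace the Day 28 condition with a visit-based one: an evaluable response assessment *at the scheduled pre-Cycle 2 response assessment or later*. All seven nominal window days then count, against one now, and the rule moves with the actual start of Cycle 2. Another fixed day would repeat the fault. A Day 22 cut-off would still miss marrows on Days 19 to 21 if Cycle 2 began on Day 26.

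The latest amendment's justification says the primary study report is finalised, so any EAP analyses already produced should be rerun under the new definition. A listing of EAP exclusions by arm, as already planned for the mITT, would show how many patients were affected.

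The cost is document wording and a rerun on data already collected. The downside for the sponsor is a slightly larger EAP with a slightly less favourable ORR.

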6. SUBJECT DISPOSITION

The total number of subjects screened for both Phase 1b and Phase 2 will be presented. The number and percentage of subjects and the failed inclusion/exclusion criteria for subjects who were screened but not enrolled or randomized will be included in the summary of screen failures. Percentage will be based on all screened subjects.

Subject disposition will be reported separately for Phase 1b and Phase 2. The disposition of subjects will be summarized with counts and percentages by dose cohort for Phase 1b or treatment arm for Phase 2 in the following four analysis populations, respectively:

- FAP (Phase 1b)
- ITT population (Phase 2)
- mITT population (Phase 2)
- Safety population (Phase 2)

Reasons for treatment discontinuation will be summarized with the following categories:

- Death
- Adverse event
- Pregnancy
- Progressive disease
- Lack of efficacy
- Withdrawal by subject
- Non-compliance with study drug
- Lost to follow up
- Study terminated by sponsor
- Transition to commercially available treatment
- Physician decision
- Disease relapse
- Symptomatic deterioration
- Allogeneic HSCT
- Protocol violation (to be specified on eCRF)
- Other (to be specified on the eCRF)

Reasons for study discontinuation will be summarized with the categories below. Same categories for study discontinuation will be summarized for subjects who continue into the follow-up phase.

- Death

- Adverse event
- Progressive disease
- Lack of efficacy
- Withdrawal by subject
- Non-compliance with study drug
- Lost to follow up
- Study terminated by sponsor
- Transition to commercially available treatment
- Physician decision
- Disease relapse
- Symptomatic deterioration
- Other (to be specified on the eCRF)

Summary of subjects enrolled by region, country and site will be provided based on all enrolled and randomized population and FAP population (Phase 1b), respectively, and ITT population (Phase 2).

Subject disposition based on the FAP population (Phase 1b) and ITT population (Phase 2) will be listed, respectively. A listing of reasons for exclusion from the mITT population will be provided based on ITT population (Phase 2). A separate listing will be provided for subjects who were not enrolled/randomized (screen failures) with reasons for screening failure.

7. PROTOCOL DEVIATIONS/VIOLATIONS

The protocol deviations/violations will be identified by sites and assessed by clinical research physician or designee following company standard operational procedure. These protocol deviations/violations will be summarized by dose cohort for the FAP population (Phase 1b) and by treatment arm for the ITT population (Phase 2).

Protocol deviations and violations will be reviewed prior to database lock for CSR. Major protocol deviations will be used to determine the mITT population for Phase 2 subjects (defined in [Section 5.2.2](#)).

Protocol deviations and violations will be summarized using frequency tabulations. A by-subject listing of subjects with all protocol deviations/violations in the FAP population (Phase 1b) and ITT population (Phase 2) will be provided.

